2.3.1. Protocol Risk Mitigation Features

Methods to minimize potential risks are relevant for participants assigned to LY3209590 Algorithm 1 and insulin degludec treatment groups. These include:

- Thorough training on the protocol design elements and inclusion/exclusion criteria; use of an electronic diary (eDiary), a web-interface, and reporting system along with availability of associated instruction manuals and reference documents.
- Careful data validation: After patient-reported data has been entered and synced remotely to the central web server, the investigator is able to view the data through the web portal and generate summary reports. An important feature of the study requires careful review of the reported information with the patient and verification of its accuracy at each study visit.
- Email notification to investigator any time the patient reports a potential severe episode of hypoglycemia (requiring assistance due to neurological impairment) in the eDiary.
- Specific criteria for fasting or persistent hyperglycemia are described protocol Section 6.1.2.3.
- Use of CGM with appropriate low/high glucose alarms throughout the study.

Importantly, in both treatment groups, the final dosing decisions remain subject to clinical judgement of the investigator. Decisions to override an algorithm recommended dose are documented in the electronic case report form (eCRF) for Algorithm 1 and insulin degludec.

3. Objectives and Endpoints

Objectives	Endpoints
Primary	

 To investigate the efficacy of LY3209590 compared with insulin degludec in study participants with T1DM 	
 HbA1c change from baseline to Week 26
Secondary	
Efficacy 
 To investigate the efficacy of LY3209590 compared with insulin degludec in study participants with T1DM 	
 HbA1c change from baseline to Week 12 Fasting glucose change from baseline to Weeks 12 and 26 Insulin dose change for bolus insulin from baseline to Weeks 12 and 26
Safety 
 To investigate the safety of LY3209590 compared with insulin degludec in study participants with T1DM 	
 Incidence and rate of hypoglycemia events during the treatment period Incidence of treatment-emergent serious AEs

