6.1.2.2. Management of Increased Hypoglycemia Risk

To date, effects of LY3209590 on hypoglycemia in patients with T2DM are not different as compared to other basal insulins. An objective of the study is to assess the risk of hypoglycemia in T1DM patients receiving LY3209590 as compared to insulin degludec.

In this study, increased risk of hypoglycemia is defined as having a single episode of severe hypoglycemia or having more than 1 episode of documented hypoglycemia with $BG < 54 \text{ mg/dL}$ within a 1-week period at any time during the treatment period. Documented hypoglycemia is defined as any time a participant reports a SMBG $\leq 70 \text{ mg/dL}$ ($< 3.9 \text{ mmol/L}$) or any investigator confirmed case of severe hypoglycemia.

In cases where a patient experiences hypoglycemia as described above, to confirm the increased risk, the study sites must ensure that the patient has been fully compliant with the assigned therapeutic regimen and also that there is no evidence of other possible causes of hypoglycemia (e.g., omission of meal, inadequate meal or correction bolus, unexpected increase in exercise).

Patients fulfilling the definition of increased risk of hypoglycemia should first correct their bolus dosing, then decrease their dose of IP per the respective dosing algorithm, followed by discontinuation of IP, if needed.

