10.8. Appendix 8: Dosing Guidance for LY3209590 and Insulin Degludec

10.8.1. LY3209590 Algorithm 1 (paper algorithm)

In Study BDCP, a paper dosing Algorithm 1 will be used by investigators for initiating and adjusting LY3209590 to achieve the target FG ≤ 100 mg/dL (< 5.6 mmol/L).

In situations where study participant safety is a concern, investigators may make adjustments to the dose of LY3209590 recommended by the dose-adjustment algorithm in Table 2; however, clinical rationale must be documented in the eCRF and Lilly Medical must be informed about this deviation and associated medical rationale. If the investigator has safety concerns about the algorithm, the investigator is to contact the Lilly CRP.

At the time of site visit, the investigator will assess the study participant's glycemic control for the previous week and, if necessary, inform the study participant about any needed dose adjustment. The dose will be based on the study participant's FG value obtained from the CGM system prior to the morning meal and hypoglycemia documented in the electronic diary in the previous week. Adherence to the dosing algorithm provided for this study is required from Visit 3 (randomization) up to Week 25 and will be monitored periodically by the study team.

General Algorithm Considerations:

- The treat-to-target FG in the algorithm is ≤ 100 mg/dL (< 5.6 mmol/L). LY3209590 dose adjustments will be determined based on the median of the FG (determined from SMBG obtained from the CGM system, referred to as SMBG below) of at least 3 days (up to 7 days) obtained in the previous week leading up to the visit.
- The LY3209590 dose may not be increased if any SMBG reading was documented at ≤ 70 mg/dL (< 3.9 mmol/L) at any time in the preceding week. Dose decreases of 0.5 mg adjustment may be permitted if multiple episodes of hypoglycemia with SMBG ≤ 70 mg/dL (< 3.9 mmol/L) were recorded, or dose decrease of 1 mg if severe hypoglycemia (requiring assistance) occurred, or if any SMBG was documented at ≤ 54 mg/dL (≤ 3.0 mmol/L) in the preceding week.
- In dosing calculations where rounding is required, round to the nearest 0.25 mg.

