The starting LY3209590 dose is determined based on both the prior basal insulin dose and baseline fasting glucose. Participants may enter the study using insulin glargine, detemir, or degludec. Consistent with product labeling these insulins may be transitioned on a unit-for-unit basis and for the purposes of this protocol are considered equivalent. Because of the long half-life of LY3209590, the change in fasting glucose response may take several weeks to reach a steady-state response; therefore, to minimize the time needed to achieve the desired target glycemic response, a loading dose strategy will be used for the first dose only. Directions are provided below to convert current basal insulin dose (in Units, U) to the dose of LY3209590 (in mg) for determination of the starting weekly dose and for dose adjustments at subsequent Visits. Examples for Visits 3-6 are provided in *italic text*.

Visit 3 (Randomization Visit):

1. Obtain the prior daily basal insulin dose of insulin glargine, detemir, or degludec assessed during the lead-in period. Calculate the "basal insulin equivalent dose" of LY3209590

(in mg) by dividing the total daily dose of basal insulin (U) by the conversion factor of 7 U/mg.

For example, if a participant uses 35 U of degludec each day, $35 \text{ U} \div 7 \text{ U/mg} = 5 \text{ mg}$ of LY3209590.

2. The dose of LY3209590 mg is then further adjusted according to median baseline fasting glucose and the participant's current basal insulin dose (U) category as shown in Table 1.

For a participant with a median BG value of 155 mg/dL, the dose adjustment for this participant currently using a 35 U dose of degludec would be +1.5 mg.

3. The loading dose is obtained by multiplying the starting total LY3209590 weekly dose (sum of basal insulin equivalent dose and the dose adjustment from Table 1) **CCI**

*In this example, $5 \text{ mg} + 1.5 \text{ mg} = \text{LY3209590 total weekly dose of } 6.5 \text{ mg}$ **CCI** for a total first dose of **CCI**. This first dose, including the loading dose, is used at Visit 3 only.*

Table 1. LY3209590 Dose Adjustment (mg) Using the Median of Baseline Fasting Glucose and Prior Basal Insulin Dose (International Units, U)

Median Baseline Fasting Glucose (mg/dL)	Median Baseline Fasting Glucose ^b (mmol/L)	LY3209590 Dose Adjustment (mg) ^a		
		Basal Insulin Dose $\leq 15 \text{ U}$	Basal Insulin Dose $16 - 30 \text{ U}$	Basal Insulin Dose $> 30 \text{ U}$
<80	<4.4	- 0.25	- 1	- 1.5

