80 - 100	4.4 - 5.5	No change	No change	No change
101 - 140	5.6 - 7.7	+ 0.25	+ 0.5	+ 0.75
141 - 180	7.8 - 10.0	+ 0.5	+ 1	+ 1.5
181 - 220	10.1 - 12.2	+ 0.75	+ 1.5	+ 2
>220	>12.2	+ 1	+2	+3

^a This dose adjustment is added to the Basal Insulin Equivalent Dose to obtain the total weekly dose of LY3209590 in mg. The starting total weekly dose of LY3209590 is increased **CCI** to obtain the first loading dose of LY3209590 necessary to reduce the time to achieve target glycemic response.

^b Conversions from mg/dL to mmol/L were rounded off to prevent overlap between threshold ranges and to address that the glucose meter displays 1 significant digit after the decimal when reporting mmol/L readings.

Visit 4 (Week 1)

1. Obtain the starting total weekly dose LY3209590 mg determined at Visit 3. (This is 1/3rd the dose administered at Visit 3.)

From the Visit 3 example, the starting LY3209590 total weekly dose was 6.5 mg.

2. Use Table 2 to determine the dose adjustment needed for Visit 4 after carefully reviewing participant's fasting glucose (3-7 days prior to visit) and hypoglycemia documented since the last LY3209590 dose.

The participant reported no hypoglycemia since the last dose of LY3209590 and had a median FG of 150 mg/dL. Using the Week 1 (Visit 4) column, the LY3209590 weekly dose should be increased by 1 mg.

6.5 mg + 1 mg = 7.5 mg LY3209590 should be administered at Visit 4.

Table 2. Weekly Dose Adjustment of LY3209590 Using the Previous Week's Dose (D) using the Median Fasting Glucose and Hypoglycemic Episodes

Median Fasting glucose (mg/dL) ^a	Median Fasting glucose (mmol/L) ^{a,e}	Week 1 (Visit 4) (2 nd dose)	Week 2 (Visit 5) (3 rd dose)	Subsequent Week ^c
<80 mg/dL or have any nocturnal hypoglycemia or multiple (≥ 3) episodes of hypoglycemia ^d	<4.4 mmol/L or have any nocturnal hypoglycemia or multiple (≥ 3) episodes of hypoglycemia ^d	D ^b – 1.5 mg	D ^b – 1 mg	D ^e – 0.5 mg
80 – 100 mg/dL	4.4 – 5.5	D ^b – 1 mg	D ^b – 0.5 mg	No change
101 – 140 mg/dL	5.6 – 7.7	No change	No change	D ^e + 0.25 mg
141 – 180 mg/dL	7.8 – 10.0	D ^b + 1 mg	D ^b + 0.5 mg	D ^e + 0.25 mg
>180 mg/dL	>10.0	D ^b + 2 mg	D ^b + 1 mg	D ^e + 0.5 mg

^a Based on median fasting glucose from at least 3 fasting glucose readings from previous week.

^b D for Week 1 (Visit 4) is ~~CCI~~ of the dose administered at (Week 0, Visit 3). D for Week 2 (Visit 5) is the dose administered at Week 1 (Visit 4).

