^c D for Subsequent Visits is the dose administered one week prior to the current visit.

^d The LY3209590 dose may not be increased if any SMBG reading was documented at ≤ 70 mg/dL (<3.9 mmol/L) at any time in the preceding week. If multiple episodes of hypoglycemia with SMBG ≤ 70 mg/dL (<3.9 mmol/L) were recorded, follow guidance for dose reduction according to the applicable Visit number. Dose decreases of 1 mg should be made when severe hypoglycemia (requiring assistance) occurred, or if any SMBG was documented at ≤ 54 mg/dL (≤ 3.0 mmol/L) in the preceding week.

^e Conversions from mg/dL to mmol/L were rounded off to prevent overlap between threshold ranges and to address that the glucose meter displays 1 significant digit after the decimal when reporting mmol/L readings.

Visit 5 (Week 2)

1. Confirm the dose of LY3209590 mg administered at Visit 4.

From the Visit 4 example, the LY3209590 weekly dose was 7.5 mg.

2. Use Table 2 to determine the dose adjustment needed for Visit 5 after carefully reviewing participant's fasting glucose (3-7 days prior to visit) and hypoglycemia documented since the last LY3209590 dose.

The participant reported no hypoglycemia since the last dose of LY3209590 and had a median FG of 153 mg/dL. Using the Week 2 (Visit 5) column, the LY3209590 weekly dose should be increased by 0.5 mg.

7.5 mg + 0.5 mg = 8.0 mg LY3209590 should be administered at Visit 5.

Visit 6 (Week 3)

1. Confirm the dose of LY3209590 administered at Visit 5 (Week 2).

From the Visit 5 example, the LY3209590 weekly dose was 8.0 mg.

2. Use Table 2 to determine the dose adjustment needed for Visit 6 after carefully reviewing participant's fasting glucose (3-7 days prior to visit) and hypoglycemia documented since the last LY3209590 dose.

The participant reported one episode of nocturnal hypoglycemia since the last dose of LY3209590 and had a median FG of 133 mg/dL. Using the Subsequent Week column in Table 2, and because of the case of nocturnal hypoglycemia, LY3209590 dose should be reduced by 0.5 mg.

8.0 – 0.5 = 7.5 mg of LY3209590 should be administered at Visit 6.

Subsequent visits are managed using the same approach as for Visit 6 (Week 3), always confirming the LY3209590 dose administered at the prior visit, the median fasting glucose during the week prior to the visits, and hypoglycemia status since the last dose of study drug.

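### Protocol 10.8.1 gives two different LY3209590 dose reductions for the same hypoglycemic event at Week 1 and from Week 3, and does not say which governs

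*Protocol*

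**What the plan says.** Four pieces of text bear on a dose reduction after hypoglycemia in the LY3209590 arm.

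- **Protocol 10.8.1, Table 2, first row.** Besides a median fasting glucose below 80 mg/dL, the row is entered if participants "or have any nocturnal hypoglycemia or multiple" episodes, with multiple set at three or more. The reduction depends on the visit: 1.5 mg at Week 1, 1 mg at Week 2, 0.5 mg later.
- **Footnote d, attached to that row.** For multiple episodes at or below 70 mg/dL, sites are to "follow guidance for dose reduction according to the applicable Visit number". The footnote then adds: "Dose decreases of 1 mg should be made when severe hypoglycemia (requiring assistance) occurred". The same 1 mg applies to any SMBG reading at or below 54 mg/dL in the preceding week. It is not tied to a visit.
- **Protocol 10.8.1, General Algorithm Considerations.** "Dose decreases of 0.5 mg adjustment may be permitted if multiple episodes of hypoglycemia with SMBG" at or below 70 mg/dL were recorded, "or dose decrease of 1 mg if severe hypoglycemia (requiring assistance) occurred" or a reading was at or below 54 mg/dL. This bullet is permissive, whereas footnote d uses 'should'. It has no visit columns and no number for 'multiple'.
- **Protocol 6.1.2.2.** Increased hypoglycemia risk is one severe event, or more than one episode below 54 mg/dL within a week. Such patients first correct bolus dosing, "then decrease their dose of IP per the respective dosing algorithm".

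**The concern.** The first row and footnote d are both written as rules, and their triggers overlap. Four combinations meet both:

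- a night-time reading at or below 54 mg/dL;
- three or more episodes, one of them at or below 54 mg/dL;
- a severe event that occurs at night or is one of three or more episodes;
- a median fasting glucose below 80 mg/dL with any reading at or below 54 mg/dL.

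If the two rules give different reductions, a site that follows the protocol's own hypoglycemia step in 6.1.2.2 arrives at two doses. Week 1 is also the first dose after the loading dose.

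There is a smaller statistical consequence. Protocol 9.4.2.4 and SAP 5.5 count prescribed doses that departed from the algorithm dose. If the algorithm dose is not unique, the reference for that count can differ between sites for the same event.

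**Working it through.** **Inputs**

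- First-row reductions at Week 1 / Week 2 / later: 1.5 / 1 / 0.5 mg (Table 2).
- Footnote d reduction: 1 mg at any visit.
- Starting dose: obtained by "dividing the total daily dose of basal insulin (U) by the conversion factor of 7 U/mg", plus the Table 1 adjustment.
- D is the starting weekly dose at Week 1 and the previous week's dose after that. The redacted loading multiple is not needed.

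**Step 1. Reproduce the protocol's example.** 35 U / 7 = 5.0 mg; Table 1 adds 1.5, giving 6.5 mg. Visit 4: 6.5 + 1 = 7.5. Visit 5: 7.5 + 0.5 = 8.0. Visit 6, after one night-time episode: 8.0 − 0.5 = 7.5 mg. All agree with the protocol. The example gives no glucose value for that episode, so it does not show what happens at or below 54 mg/dL.

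**Step 2. Confirm the overlap.** Section 6.1.2.2 takes documented hypoglycemia as SMBG at or below 70 mg/dL. A night-time reading at or below 54 mg/dL is therefore also night-time hypoglycemia, and both rules are met.

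**Step 3. Apply both rules to the example doses.**

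| Visit | D (mg) | First row | Footnote d | Larger / smaller |
|---|---|---|---|---|
| Week 1 | 6.5 | 6.5 − 1.5 = 5.0 | 6.5 − 1 = 5.5 | 5.5 / 5.0 = 1.10 |
| Week 2 | 7.5 | 7.5 − 1 = 6.5 | 7.5 − 1 = 6.5 | 1.00 |
| Week 3 | 8.0 | 8.0 − 0.5 = 7.5 | 8.0 − 1 = 7.0 | 7.5 / 7.0 = 1.07 |

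**Step 4. Other starting doses (illustrative).** The gap is always 0.5 mg. The ratio is (D − 1)/(D − 1.5) at Week 1 and (D − 0.5)/(D − 1) from Week 3, and both fall as D rises. The documents give no distribution of basal doses, but Table 1 has columns for 15 U or less and for 16 to 30 U. I assume a baseline median fasting glucose of 80–100 mg/dL (no Table 1 change). For the Week 3 figures I assume 101–140 mg/dL at Weeks 1 and 2 (no Table 2 change).

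| Basal dose | D (mg) | Week 1: first row vs footnote d | Week 3: first row vs footnote d |
|---|---|---|---|
| 28 U | 28 / 7 = 4.0 | 2.5 vs 3.0 (ratio 1.20) | 3.5 vs 3.0 (ratio 1.17) |
| 14 U | 14 / 7 = 2.0 | 0.5 vs 1.0 (ratio 2.0) | 1.5 vs 1.0 (ratio 1.5) |

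**Step 5. Can the intent be inferred?** If footnote d overrides the row, then at Week 1 a night-time reading at or below 54 mg/dL gets a smaller reduction (1 mg) than a milder night-time episode (1.5 mg). If the row overrides the footnote, then from Week 3 a night-time reading at or below 54 mg/dL gets 0.5 mg, while a single daytime reading that low gets 1 mg. Either simple order produces an inversion, so a site cannot deduce which was meant. Nothing in the text supports adding the two reductions, so I give no additive figure.

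**The case against.** The best counter-argument is that the general bullet and footnote d share a graded structure: one reduction for multiple episodes, 1 mg for a severe event or a reading at or below 54 mg/dL. From Week 3 the Table 2 column for multiple episodes is itself 0.5 mg, so the bullet and the footnote line up and suggest that 1 mg governs. This carries some weight for repeated episodes. It remains inference: the bullet is permissive, omits night-time episodes, states no precedence and leaves Week 1 unexplained.

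A second argument is that footnote d must already displace the other rows of Table 2. For example, at Week 2 with fasting glucose 80–100 mg/dL and one reading at or below 54 mg/dL, the row gives 0.5 mg and the footnote 1 mg. So why not read it as displacing the first row too? Those other rows contain no hypoglycemia trigger. The first row has its own trigger and its own visit-specific reductions, so there the two rules compete. If the override reading is rejected throughout, the inconsistency becomes wider, not narrower.

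Third, the size. The larger percentages rest on an assumed 14 U participant, the relative gap shrinks above 35 U, and no event frequency is given. The ratios describe the next injection, not exposure; at 14 U the first dose would have been 3 × 2.0 = 6.0 mg, since Visit 4 puts the weekly dose at one third of it. All of this stands, and the half-life is redacted, so exposure cannot be computed.

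Fourth, the safeguards are real. Under Protocol 2.3.1 "the final dosing decisions remain subject to clinical judgement of the investigator". Severe events are SAEs reported within 24 hours (8.3.7.1, 8.3.1), the sponsor may modify the guidance (4.3), and the unblinded study team may advise on dose (SAP 6). They reduce the risk, but they work as departures from, or changes to, an algorithm dose that the text does not define uniquely.

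**Conclusion.** The concern holds. When both sets of triggers are met, Protocol 10.8.1 yields two doses 0.5 mg apart at Week 1 and again, in the opposite direction, from Week 3; at Week 2 they agree. In the protocol's own example the doses are 10% apart at Week 1 and 7% apart at Week 3. Over the illustrative range 14–35 U the gap runs from 10% to two-fold at Week 1 and from 7% to 50% at Week 3, under the glucose assumptions in Step 4.

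The 0.5 mg in the general bullet for multiple episodes is a lesser matter. Footnote d and the visit-by-visit steps show that Table 2 is the operative rule, so the bullet is an unaligned summary rather than a second rule.

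The adherence consequence is limited to a descriptive count, and I claim no effect on the primary analysis. The text still needs correcting because the ambiguity sits in the step on which the protocol relies after hypoglycemia. I take no view on which reduction is right.

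**What to change.** Reconcile the general bullet, the first row of Table 2 and footnote d in Protocol 10.8.1 so that:

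- each trigger gives one reduction in each visit column;
- the text says which rule applies when several triggers are met;
- the reduction for a severe event or a reading at or below 54 mg/dL is worded once, as either permitted or required;
- 'multiple' has the same definition throughout (only the general bullet lacks the number).

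The sponsor's clinical team must set the values; none is proposed here.

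For the counts in Protocol 9.4.2.4 and SAP 5.5, use the reconciled rule as the reference prospectively, and do not re-judge doses already given under the present text.

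The cost is a wording amendment to Appendix 8, with the IRB/IEC approval required by Protocol 10.1.1 and notice to sites. SAP 5.5 needs one sentence giving the date from which the reconciled rule is the reference. No new data are needed.

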10.8.2. Insulin Degludec

A dosing algorithm (adapted from Riddle et al. 2003) will be used by investigators for initiating and adjusting insulin degludec to target an FG ≤ 100 mg/dL (< 5.6 mmol/L) for patients to achieve glycemic goal.

In situations where patient safety is a concern or where dose adjustments have not had the desired therapeutic effect, investigators may make increased or decreased adjustments to the dose of insulin degludec recommended by the dose-adjustment algorithm and have to document the clinical rationale for the deviation as well as inform Lilly medical per email.

At the time of site visit or telephone visit, the investigator will assess the patient's glycemic control for the previous week and, if necessary, inform the patient about any needed dose adjustment. The dose will be based on the patient's BG value. Adherence to the dosing algorithm provided for this study is mandatory from Visit 3 (randomization) up to Visit 20 (Week 26), inclusive. Dose increases may be made at weekly intervals and no sooner than 5 days following the last dose increase. In some cases, patient visits could occur sooner than 5 days apart due to the allowable visit window; however, there should be no dose increase if at least 5 days have not elapsed since the previous dose increase. In contrast, the insulin degludec dose may be reduced at any time on the judgment of the investigator. Any deviations from this guidance must be supported by clinical evidence and after consultation with Lilly Medical.

Insulin dose algorithms have been reviewed by Strange (2007). The insulin degludec dose increase algorithm is adapted from Riddle et al. 2003 and will be determined based on the definition of what is termed the "Algorithm FG." The Algorithm FG is the median of the FG (determined from SMBG) of Days 5, 6, and 7 since the last insulin dose increment. If the

interval since the last dose adjustment has been longer than 7 days, the dose increase is determined by the median of the FG of the last 3 days. If the patient only measured their FG on 2 of the last 3 days, then the lesser of those 2 FG values should be used as the Algorithm FG. If only 1 FG measurement is available for the last 3 days, then the investigator should use his/her discretion in determining whether there should be a dose adjustment based on that single FG value.

As it is desired to achieve glycemic goals in as many patients as possible, contingencies are provided to accommodate prespecified protocol visits and to increase the dose of insulin degludec in a timely manner. Therefore, if the last dose increment was 5 days previous, then the dose increment is determined by the Algorithm FG, which is the lesser of the 2 FG values from Day 4 and Day 5. If the dose increment was 6 days previous, then the Algorithm FG is the lesser of the 2 FG values from Day 5 and Day 6. In both of these cases, if only 1 of the 2 FG values is available, then the investigator should use his/her discretion in determining whether there should be a dose adjustment based on that single FG value.

The dose increase algorithm is defined as follows:

- If the Algorithm FG is 101 to 120 mg/dL (5.6 to 6.7 mmol/L), increase the dose by 2 U
- If the Algorithm FG is 121 to 140 mg/dL (6.8 to 7.8 mmol/L), increase the dose by 4 U
- If the Algorithm FG is 141 to 180 mg/dL (7.9 to 10.0 mmol/L), increase the dose by 6 U
- If the Algorithm FG is >180 mg/dL (10.0 mmol/L), increase the dose by 8 U

The treat-to-target FG is \leq 100 mg/dL (<5.6 mmol/L). The insulin degludec dose will not be increased if any SMBG was documented at \leq 70 mg/dL (<3.9 mmol/L) at any time in the preceding week. Dose decreases of 2 to 4 U per adjustment may be permitted if multiple episodes of hypoglycemia with SMBG \leq 70 mg/dL (<3.9 mmol/L) were recorded, if severe hypoglycemia (requiring assistance) occurred, or if any SMBG was documented at \leq 54 mg/dL (≤3.0 mmol/L) in the preceding week.

